Black ^a	98 (36.3)	47 (17.4)	125 (46.3)
White	515 (59.3)	96 (11.0)	258 (29.7)
Other	101 (52.3)	20 (10.4)	72 (37.3)

^a Significantly more "not sure" vs. "yes" and "no" vs. "yes" than all other groups

B. INNOVATION

B1. This is one of the first studies to address barriers to the uptake of the COVID-19 vaccine in pediatric populations. While interventions targeting vaccine uptake related to other diseases in pediatric populations and COVID-19 vaccine uptake in adult populations exist, no published studies describe strategies to increase COVID-19 vaccine uptake in pediatric populations. Although a vaccine is not yet approved for

children under age 16, it is important to proactively mitigate barriers to vaccination and pre-register children now for the COVID-19 vaccination. This will expedite vaccine delivery when it becomes available in the near future. Finally, while much can be learned from strategies to increase COVID-19 vaccine uptake among adults, there are likely key differences that will need to be addressed when designing an intervention for children and families. For instance, education must be tailored to both caregivers and children and factors influencing caregivers treatment decisions for their child differ from those influencing decisions for themselves.

B2. This intervention will address multiple factors that contribute to disparities in COVID-19 vaccine uptake using best practice community based participatory research methods and innovative crowdsourcing methods to ensure that the intervention is relevant and acceptable to Black and Latino communities. As seen with vaccine interventions for other diseases like influenza and HPV, the most effective interventions are multicomponent and tailored to specific populations. We will leverage Nemours' existing marketing strategies and digital technologies to develop messaging that is specific to the concerns of the community, delivered by trusted members of the community, and in a format that will have the greatest reach and impact. We will also leverage Nemours' community healthcare workers and large primary care network to increase access to the intervention to communities across the state of Delaware.

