Officer for Nemours Children's Health System; **2) [name], MPH**, Director of the Christiana Care Harrington Value Institute Community Partnership Fund and Harrington Trust Physician Scholar; **3) [name]**, Director of the University of Delaware (UD) Partnership for Healthy Communities and Professor of Practice and Distinguished Health and Social Services Administrator; and **4) [name]**, Attending Physician in the Nemours Division of Infectious Disease to provide expertise on the public health response to the pandemic. Finally, this project leverages robust resources offered by the Nemours Primary Care Network (Director **[name]**, co-investigator), and the Nemours Office of Health Equity and Inclusion (Research Associate **[name], BSPH, MPH**, co-investigator). Nemours Marketing and Center for Health Delivery Innovation (CHDI) will help create intervention prototypes and final intervention components.

C3. PARTNER ENGAGEMENT PLAN. To create a culturally-tailored and community-informed intervention, community and healthcare stakeholders (Table 2) will be engaged as research partners. Identification and engagement of partners will be facilitated by the UD Partnership for Healthy Communities ([name]) and Harrington Value Institute Community Partnership Fund ([name]). This Council of Community and Healthcare Partners will meet regularly throughout the course of the study with our team of investigators. Best practices from the Promising Practices Guide developed by the University of New Mexico's Engage for Equity team will be followed to ensure that community partner engagement is successful.¹⁷⁻²⁰ In addition, three FYREworks training modules²¹ (30 minutes each) will be completed by all community and healthcare partners prior to the first meeting to foster an understanding of their role in the research process.^{18,20} The quality of the research partnership will be evaluated using Engage for Equity's Community Engagement Survey²⁰ following every meeting to ensure partner synergy and alignment of values, modifying our community engagement practices as needed based on responses.

C4. STUDY DESIGN. Please see PHS Human Subjects & Clinical Trials form for detailed eligibility criteria, sample size justification, recruitment/retention plan, timeline, human subjects protection, participant compensation, and data/safety monitoring.

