PARTICIPANTS: We will extract an EHR report containing the following variables for identifying potentially eligible youth and caregivers: child and caregiver name, child race and ethnicity, child gender, child age, caregiver preferred language, caregiver contact information, child’s COVID-19 vaccination status, insurance type, and primary care site. Youth (n = 20-30) between 12 and 17 years old who receive their medical care at a Nemours primary care practice, identify as Non-Hispanic Black or Latina/o, and are proficient in English or Spanish will be recruited. Similarly, caregivers (n = 20-30) will be recruited if they are proficient in English or Spanish and are the legal guardian of a child between 5 and 17 years old who receives medical care at a Nemours primary care practice and identifies as Non-Hispanic Black or Latina/o. Potentially eligible participants will be recruited by phone or in-person at clinic visits from an EHR-generated list or by flyers

posted at community organizations serving teens from Black and Latino communities. For participants recruited by phone or flyer, all follow-up efforts will be made by phone, text, and/or email, advising participants to contact the research team to learn more about or opt out from the project (see attached materials for each recruitment method). During the initial screening phone call or in-person visit with interested potential participants, a research coordinator will provide a brief description of the study, confirm eligibility, and confirm interest in study participation. For eligible participants who are interested in participating, demographic information will be

confirmed and entered into REDCap and a secured REDCap survey link hosting an electronic consent and/or assent form will be sent to the participant or pulled up on a secure tablet used only for research purposes. The research coordinator will complete the consent process over the phone or in-person with the participant. Youth will be able to participate if their caregivers do not and vice-a-versa. To ensure that the intervention components are sufficiently evaluated for both English and Spanish-speaking families, recruitment will be stratified by language and race/ethnicity. Based on the research team’s experience in previous studies,²⁶⁻²⁸ a sample size of 10-15 youth and 10-15 caregivers from each language group is anticipated to be sufficient to

Table 4. Qualitative Analysis

Step	Example Prototype

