INTERVENTION REFINEMENT: Ratings on the AIM range from 1 to 5, with higher scores indicating greater acceptability. A score of 4 indicates that participants "agree" that interventions are acceptable. Intervention components with a mean score < 4 will be modified based on qualitative responses, with the research team determining what modification can be made based on importance and feasibility. The process of revision and participant feedback will continue until the mean acceptability score is ≥ 4 .

AIM 3. Test the preliminary efficacy of the intervention through a pilot cluster randomized controlled trial of the intervention at 4 Nemours primary care sites.

[figure not shown]
PARTICIPANTS: Four primary care practices will be enrolled in the study (Figure 4), leveraging RPL [name]'s prior work with primary care practices in Delaware and co-I's [name] role as Director of the Nemours Primary Care Network. The four primary care practices selected for the study have large and diverse patient populations, with two practices in Northern Delaware (Becks Woods, Foulk Road) and two in Southern Delaware (Milford, Seaford) having comparable patient demographics. All practices are within the Nemours Children's Health System, which provides care to the majority of children in the state, and share an EHR.

STUDY DESIGN: A pilot cluster randomized controlled trial will be conducted, with clustering at the practice level. Enrolled practices will be randomly allocated to receive the intervention (Intervention Practice) or not (Control Practice) using a 1:1 randomization scheme stratified by practice location (Northern or Southern Delaware).

OUTCOME MEASURES

Vaccination Rates: We will extract EHR data about rate of COVID-19 vaccination for all eligible children at each practice.

Accountability for Vaccination: Vaccination rates for each site will be made available and reviewed monthly by the Nemours Primary Care

Network, who will share an overview of de-identified data with the Delaware Division of Public Health and partner with them to ensure that enough COVID-19 vaccines will be allocated and distributed to communities to meet demand and that continual efforts to encourage vaccination.

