Disparities: Child race/ethnicity (Black, White, Latino, Other) will be the primary measure of disparity and will be collected from the EHR. Zipcode from the EHR will be used to categorize patients into rural vs. not (RUCA ≥4)⁴⁰ and to generate a Child Opportunity Index score⁴¹ for each child as secondary measures of disparity. Insurance, sex, medical diagnoses, and caregiver preferred language will also be collected from the EHR.

ANALYSES: Analyses demonstrated the efficiency of the stratified cluster randomized trial in detecting a difference in vaccination rate of 30% among Blacks in the Control Practices compared to an increase in vaccination rate to 60% among Blacks in Intervention Practices, with a sample size of 500, $\alpha < 0.05$ and power of 90%. Proportions of caregivers who vaccinate their child will be compared by level of intervention using chi-square tests. To test the efficacy of the intervention, while accommodating the cluster-randomized design of the study, a multi-level mixed-effects model (MME) logistic regression will be used fit to the data for the primary outcome of child vaccination rate to assess the effect of intervention. MME models will be adjusted for race/ethnicity to evaluate the effect of intervention on reducing this disparity.

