C5. POTENTIAL CHALLENGES AND ALTERNATIVE APPROACHES. The state of the COVID-19 pandemic is evolving rapidly. By the time the project begins, more vaccines may become available and to younger age groups; however, we are certain that there will still be families who are unsure of whether to vaccinate their children against COVID-19 or who face barriers to access. As vaccines become more available to children, Nemours Marketing may begin to develop COVID-19 vaccination campaign or registration materials. In this case, we will work closely with them to ensure that the preliminary data we've collected from families and the input of our community partners is considered. Any early development of COVID-19 materials will only expedite our development process since prototypes will already be available. However, it will still be critical to conduct the process of refining and testing any intervention to ensure it is tailored to the needs and values of communities and families. Our ongoing engagement with community partners will also ensure that we are nimble in adapting our approach to be responsive to any other changes in how families are experiencing the pandemic. Finally, it is possible that the reach of the intervention may not extend to as many families in the community as intended with our pilot trial. Therefore, it will be important for us to gather data on the number of families who access different intervention components (e.g. data analytics for digital components, number of families who attend an event). This data can be used to determine intervention reach and provide insight into which components are most impactful.

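### Child age is neither a named covariate in the Aim 3 primary model nor a listed Aim 3 variable, although vaccine availability depends on age and only four practices are randomised

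*Combined protocol and SAP*

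**What the plan says.** All references are to the combined protocol and SAP.

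- **Model (Section C4, Aim 3, Analyses).** The plan states that "a multi-level mixed-effects model (MME) logistic regression will be used fit to the data for the primary outcome of child vaccination rate". The only covariate named is race/ethnicity: "MME models will be adjusted for race/ethnicity to evaluate the effect of intervention on reducing this disparity". Unadjusted chi-square comparisons are also planned.
- **Variables (Aim 3, Disparities).** Race/ethnicity is the primary disparity measure. Zip code yields rurality and the Child Opportunity Index. Then: "Insurance, sex, medical diagnoses, and caregiver preferred language will also be collected from the EHR". Age is not listed.
- **Outcome population (Aim 3, Vaccination Rates).** "We will extract EHR data about rate of COVID-19 vaccination for all eligible children at each practice". No age range is given here. Section C4 opens by deferring such detail to a form that is not part of the documents: "Please see PHS Human Subjects & Clinical Trials form for detailed eligibility criteria, sample size justification".
- **Where age does appear.** The Aim 2 recruitment report from the EHR includes "child race and ethnicity, child gender, child age, caregiver preferred language". Aim 2 covers caregivers of children aged 5 to 17.
- **Age and vaccine availability.** Section A.3 describes early vaccination clinics for patients over 16. Section B1 says that a vaccine was not yet approved for "children under age 16, it is important to proactively mitigate barriers to vaccination and pre-register children now for the COVID-19 vaccination". Section C5 expects that by project start "more vaccines may become available and to younger age groups".
- **Randomisation (Aim 3, Participants and Study Design).** Four practices, two northern and two southern, are allocated 1:1 within region. The text says that their patient populations are alike but gives no age distribution.

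**The concern.** If availability opens at different times for different ages, age determines how long a child has had to be vaccinated. It is then likely to be a strong predictor of the outcome, whatever the family's attitude or the practice's efforts. A predictor of that kind matters in two ways when whole practices are randomised. Differences in age mix add to the variation between practices, and so to the uncertainty of the intervention effect. In the one randomisation actually carried out, the arm with more long-eligible children starts with an advantage that has nothing to do with the intervention.

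With one practice per arm in each region there is little averaging to smooth this out. A child-level covariate can remove much of it without using practice-level degrees of freedom, but it has to be in the extract and named in advance. If age is added after the uptake figures have been seen, the choice will look data-driven.

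**Working it through.** **The plan's own figures.** The target difference is 60% − 30% = 30 points, among Black children, with N = 500, alpha 0.05 and 90% power. Without clustering, a two-sided test of 30% against 60% needs 56 per arm, 112 in total. N = 500 would correspond to a design effect of 500/112 = 4.46. With 125 children per practice, that is an ICC of (4.46 − 1)/(125 − 1) = 0.028. No ICC is stated, so 500 can be neither confirmed nor called wrong. Age adjustment does not enter that calculation. The 30-point difference serves below only as a yardstick.

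**What is assumed.** The documents give neither age mix by practice nor uptake by age. Two inputs are therefore assumptions:
- s, the SD between practices *within a region* in the share of older (longer-eligible) children: 5 to 10 points. Differences between North and South do not count, because stratification removes them.
- g, the difference in uptake between the older and younger bands: 20 to 40 points.

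**Step 1: number of allocations.** Two regions with two possible assignments each give 2 × 2 = 4.

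**Step 2: chance difference in age mix.** Each arm's mean is the average of two practices, one per region. The SD of the arm difference is s × sqrt(1/2 + 1/2) = s, so 5 to 10 points.

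**Step 3: how often the arms differ noticeably.** Using a normal approximation, confirmed by simulation for the rows shown:

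| Assumed s | Arms differ by more than 5 points | By more than 10 points |
|---|---|---|
| 5 points | about 32% | about 4.5% |
| 10 points | about 62% | about 32% |

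If s were only 3 points, a difference above 5 points would occur in just under 10% of randomisations.

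**Step 4: effect on the arm comparison of uptake.** Chance arm difference = g × (difference in older share), so its SD is g × s.
- Low end: 0.20 × 0.05 = 0.01, or 1 point; 1/30 = 3% of the planned difference.
- High end: 0.40 × 0.10 = 0.04, or 4 points; 4/30 = 13%.
- 95% range (1.96 × SD): about ±2.0 to ±7.8 points.

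**Step 5: the unadjusted chi-square tests.** Take 250 children per arm, a 30% base rate and no intervention effect. A fixed 4-point difference due to age would lead to rejection in favour of the older arm about 16% of the time, and an 8-point difference about 47%, against a nominal 2.5% in that direction. These rates describe the secondary, unclustered test, conditional on that imbalance. They do not describe the primary mixed model.

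**The case against.** The strongest reply has five parts.

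**Balance.** The practices were chosen as demographically similar and paired by region, so only within-region differences matter. This stands. A reader might infer that randomisation cannot balance age here, or gives almost no protection. The documents do not support that. They show no imbalance, only the absence of age figures that would settle the question.

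**Bias.** Under randomisation, chance imbalance averages zero. It is part of the between-practice variance that the multilevel model is meant to carry into the standard error. This also stands: a reader might conclude that the primary estimate is biased, but what is shown is a loss of precision and exposure to an unlucky draw. Four practices give little information for estimating that variance, but that is a separate problem.

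**Unseen material.** The Aim 3 age range may be in the external form. If the cohort is a single age band, or all bands had long been eligible, the mechanism shrinks. True, but an age restriction there would not put an age term in the model described here.

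**The variable list.** It is not presented as exhaustive, and finding eligible children in the EHR would presumably require age. So it would be wrong to infer that age will not be available. The gap is that neither the listed variables nor the named covariates include it.

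**Size.** Against 30 points, an SD of 1 to 4 is modest, and this is a pilot. That limits the weight of the point. The true effect may, however, be smaller than planned, and Section C7 intends the result to support a larger trial.

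**Conclusion.** The point holds in a limited form. In the documents supplied, race/ethnicity is the only covariate named for the primary model and child age is not a listed Aim 3 variable, while the protocol itself ties vaccine availability to age and leaves the Aim 3 age range unstated. One practice per arm per region cannot be relied on to balance age mix.

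The size, an SD of 1 to 4 percentage points in the arm difference, is illustrative. It rests wholly on the two assumed ranges and scales in proportion to each; real age shares from the four practices could make it smaller or larger. It would not by itself explain a 30-point difference, but it could matter for a materially smaller one. The change is worth making because it is inexpensive and must be made before outcomes are seen. It is not grounds for calling the design invalid, and it leaves the four-cluster inference problem where it was.

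**What to change.** 1. Add child age to the stated Aim 3 EHR variables, and state the age range of the outcome population in the analysis section.
2. Prespecify age band as a child-level covariate in the primary mixed-effects logistic model, alongside race/ethnicity. Split the bands by when each age group became eligible for vaccination. The documents do not give those dates, so the sponsor should fix them in the SAP before looking at outcomes.
3. Report age mix by practice and by arm at baseline. The practices share an EHR, so the assumed ranges used here can be replaced by actual figures.
4. Optionally, add insurance and preferred language, which are already to be collected, as secondary or sensitivity covariates.
5. Report a standardised (marginal) risk difference beside the odds ratio.

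The cost is SAP wording, one field that the study already draws from the EHR for Aim 2, and slightly more analysis work. There is one technical consequence: in logistic regression an added prognostic covariate changes the conditional odds ratio being estimated, which item 5 addresses.

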Improving COVID-19 Vaccine Uptake Among Black and Latino Youth
NCT 05293392
December 6, 2021

A. SIGNIFICANCE

A.1 BACKGROUND

Black and Latino communities have experienced higher rates of COVID-19 transmission, morbidity and mortality, as well as greater economic hardships due to the pandemic.^{1,2} COVID-19 vaccines can mitigate the health and economic impact of the pandemic; however, Black and Latino adults have experienced reduced rates of COVID-19 vaccination, perpetuating disparities.³ In Delaware, 15% of Blacks and 13% of Latinos have been fully vaccinated for COVID-19 compared to 21% of Whites.⁴ Racial and ethnic disparities also exist in vaccination rates for other infectious diseases (e.g., HPV, influenza) in both adult and pediatric populations.^{5,6} **Without intervention, current disparities in vaccination rates are likely to impact Black and Latino youth** for whom COVID-19 vaccines will soon become available and among whom COVID-19 vaccination is critical to reducing community transmission.

There are multiple factors that contribute to disparities in vaccination rates. Vaccine hesitancy, which is impacted by many factors including individual beliefs about the disease, attitudes about vaccination, and influential cues to action, can affect an individual's intention to vaccinate.^{7,8} In early large-scale surveys during the pandemic, Black and Latino adults expressed more hesitancy about getting the COVID-19 vaccine compared to White adults.⁹⁻¹¹ **Increasing awareness about the benefits and safety of the COVID-19 vaccine is therefore an important component to any intervention to improve COVID-19 vaccine uptake.** However, interventions to reduce vaccine hesitancy alone are unlikely to be effective at reducing disparities in vaccination rates. Many people in underserved communities also have difficulty accessing vaccines due to systemic factors (e.g., cost, insurance, time, transportation, and technology challenges).^{12,13} **Therefore, any intervention to reduce disparities in COVID-19 vaccine uptake must also reduce barriers to vaccine access and ensure equitable allocation of vaccines to communities.**

A.2 RIGOR OF PRIOR RESEARCH

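### The disparity analysis only adjusts for race/ethnicity: one common odds ratio cannot show a change in disparity, and no vaccination percentages by race and arm are planned

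*Combined protocol and SAP*

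**What the plan says.** All of the analysis text is in section C4, Aim 3, Analyses.

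- **Target.** The power statement concerns "detecting a difference in vaccination rate of 30% among Blacks in the Control Practices compared to an increase in vaccination rate to 60" per cent in Intervention Practices.
- **Primary model.** "a multi-level mixed-effects model (MME) logistic regression will be used fit to the data for the primary outcome of child vaccination rate". Efficacy is judged from this model.
- **Disparity.** "MME models will be adjusted for race/ethnicity to evaluate the effect of intervention on reducing this disparity". No interaction, contrast or scale is named. Under Outcome Measures, race/ethnicity (Black, White, Latino, Other) is called the primary measure of disparity, again without a scale.
- **Percentage-scale step.** "Proportions of caregivers who vaccinate their child will be compared by level of intervention using chi-square tests". This is by arm, not by race.
- **Background.** A.1 states: "In Delaware, 15% of Blacks and 13% of Latinos have been fully vaccinated for COVID-19 compared to 21% of Whites". A.3 and its Table 1 give percentages for response to a scheduling message and for intention to vaccinate.

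**The concern.** Whether the intervention reduces a disparity is a question about whether its effect differs between racial/ethnic groups. A main effect for race/ethnicity does not address it: it lets the groups start at different levels but gives all of them the same intervention odds ratio. Read as written, the model returns no estimate of change in disparity.

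Scale is the second part of the problem. The target and the main background disparities are percentages, while the model coefficient is a log odds ratio conditional on practice and race/ethnicity. An unchanged disparity in odds can be a wider or a narrower gap in percentages, depending on the starting rates. If no measure is named beforehand, the description of the disparity result can be chosen after the data are seen. Reducing the disparity is a central purpose of the project, and C7 expects the results to support wider use and a larger trial.

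**Working it through.** **1. The plan's own figure.** Inputs: 30% v 60%, alpha 0.05, power 90%, N = 500. For independent observations, two-sided, without continuity correction:

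n per arm = [1.96·√(2·0.45·0.55) + 1.2816·√(0.3·0.7 + 0.6·0.4)]² / 0.30² = 55.7, so 56 per arm and 112 in total.

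Reaching 500 needs a design effect of 500/112 = 4.46. With an assumed 125 children in each of four practices, that is an intracluster correlation of (4.46 − 1)/124 = 0.028. The plan states none, so 500 cannot be reproduced from its inputs. The present point does not depend on that figure.

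**2. What the stated model can estimate.** Adjustment for race/ethnicity gives

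logit p = a + practice effect + b·(Intervention) + c(race).

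The Black:White odds ratio is exp(c_Black − c_White) in both arms. The change in disparity on the odds scale is zero by construction, whatever the data show.

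**3. What a common odds ratio means in percentages.** The target implies OR = (0.60/0.40)/(0.30/0.70) = 3.5, against a rate ratio of 2.0. Apply p1 = OR·p0/(1 − p0 + OR·p0) to the document's rates. These examples treat the conditional odds ratio as if it applied to overall rates.

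| Source | Before | After, OR 3.5 | Gap (points) |
|---|---|---|---|
| A.1, Black v White | 15% v 21% | 38.2% v 48.2% | 6.0 to 10.0 |
| A.1, Latino v White | 13% v 21% | 34.3% v 48.2% | 8.0 to 13.9 |
| Table 1 intention, Black v White | 36.3% v 59.3% | 66.6% v 83.6% | 23.0 to 17.0 |

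In the first row the Black:White rate ratio goes from 15/21 = 0.71 to 38.2/48.2 = 0.79. The absolute gap widens while the relative one narrows.

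**4. At the planning point.** Black control rate 30%, OR 3.5, White control rate not given, so varied.

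- Black children rise by 30 points.
- A White rate of 40% becomes 1.4/2.0 = 70%, also a rise of 30 points, so the gap is unchanged.
- The largest rise is at (√3.5 − 1)/(3.5 − 1) = 34.8%, which becomes 65.2%. The gap then widens by 0.33 points.
- Above 40% the gap narrows.

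With smaller common odds ratios the widening range is broader: White rates up to about 54% at OR 2.0 and about 61% at OR 1.5, by about 1 point at most.

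**5. With an interaction term added.** Assume OR 3.5 in Black and 3.2 in White children, from 15% v 21%. White becomes 0.672/1.462 = 46.0% and Black 38.2%. The gap goes from 6.0 to 7.8 points, while the Black:White odds ratio moves from 0.66 to 0.73. The term makes a change estimable, but the scale still has to be named.

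**The case against.** Planning on two percentages and testing with a logistic model is ordinary practice, and the documents do not contradict themselves by doing so. Several points on this side stand.

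- A reader might infer that the efficacy result will not appear in percentages at all. The chi-square step compares proportions by arm, so uptake will stand beside the model result. It ignores clustering and is not by race, so it does not answer the disparity question.
- A reader might infer that the plan would report a widening disparity as a reduced one. The documents do not support that. The stated model cannot give a reduced reading on the odds scale, and the Aim 3 disparity outcome has no stated scale. In the low-baseline example the rate ratio moves towards equality. Treating the percentage-point gap as the only valid test would be the critic's preference.
- It would also be wrong to say that the plan always describes disparity in percentages. A.3 describes some differences only as greater or lesser likelihood, and the Table 1 footnote contrasts response categories.
- The A.1 rates are statewide, not those of children in control practices, and Table 1 records intention. At the planning rate the widening is negligible.
- The adjustment wording may be loose shorthand for a model that does include an interaction. If so, the plan needs to say so.

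None of this supplies an estimate of change in disparity, on any scale.

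**Conclusion.** The concern holds in a limited form. As written, the disparity analysis cannot show a change on the odds scale, and the plan derives no percentages by race and arm. The missing race-by-intervention term is the main fault; the unnamed scale is secondary and remains after the term is added.

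The size depends on baseline. It is material at the A.1 rates (a 6-point gap becomes 10 under a common odds ratio of 3.5), goes the other way at the Table 1 rates (23 to 17 points), and is at most 0.33 points at the 30% planning rate with the same odds ratio. This rests on a literal reading of the adjustment and on background rates standing in for control-practice rates, which the documents do not give. It is a matter of analysis and reporting, not a flaw in the trial's conduct.

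**What to change.** Keep the logistic mixed model and amend the Analyses paragraph as follows.

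1. Add a race/ethnicity-by-intervention term (three coefficients for the four categories). Percentages predicted without it would carry a change in gap imposed by the logistic curve, as in step 3, and not estimated from the data.
2. From that model, report vaccination percentages by arm and by race/ethnicity. Report the percentage-point difference between arms, standardised to a common race/ethnicity mix.
3. Define change in disparity as the Black-White and Latino-White gaps in Intervention minus those in Control. Report it beside the ratio of odds ratios and the rate ratios.
4. State that any disagreement between absolute and relative conclusions will be reported as such, with neither made the sole criterion.

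The cost is one extra model term and a post-estimation step; no new data are needed. The real limit is precision. With four practices allocated 1:1 there are two per arm, and delta-method or cluster-bootstrap intervals are unreliable at that number. The gap contrasts should be presented as imprecise and descriptive.
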